### **13.5.1 Evaluation of Target Lesions by irRECIST**

Tumor burden = Sum of diameter (target) + Sum of diameter (new)

Complete Response (CR): Disappearance of all target lesions. Any pathological lymph nodes (whether target or non-target) must have reduction in short axis to <10 mm.

Partial Response (PR): At least a 30% decrease in the tumor burden compared with baseline.

Progressive Disease (PD): At least a 20% increase in the tumor burden compared, taking as reference the smallest sum on study (this includes the baseline sum if that is the smallest on study), with confirmation of progression by a scan at least 4 weeks later (Note: With irRECIST, the appearance of new lesions alone is not considered progression).

Stable Disease (SD): Neither sufficient shrinkage to qualify for PR nor sufficient increase to

qualify for PD, taking as reference the smallest sum diameters while on study.

### **13.5.2 Evaluation of Best Overall Response with irRECIST**

The best overall response is the best response recorded from the start of the treatment until disease progression/recurrence (taking as reference for progressive disease the smallest measurements recorded since the treatment started). The patient's best response assignment will depend on the achievement of both measurement and confirmation criteria.

Measurable Response	Nonmeasurable Response		Overall Response
Total Measurable Tumor Burden	Non-Index Lesions	New Nonmeasurable Lesions	Using irRECIST
100% Decrease	Absent	Absent	irCR
≥ 30% Decrease	Any	Any	irPR
<30% Decrease to <20% Increase	Any	Any	irSD
≤ 20% Increase	Any	Any	irPD

## **13.6. Analysis of Endpoints**

Efficacy and safety endpoints that will be evaluated are listed below.

### **13.6.1 Efficacy Endpoints**

#### **13.6.1.1 Primary Efficacy Endpoint**

- Progression-Free Survival
  - PFS is defined as the time from the first day of trial treatment to the first documented disease progression per RECIST 1.1 or death due to any cause, whichever occurs first.

#### **13.6.1.2 Secondary Efficacy Endpoints**

- Objective Response Rate
  - ORR is defined as the proportion of the subjects in the analysis population who have a CR or PR. Responses are based on assessments per RECIST 1.1.
- Duration of Response
  - For subjects who demonstrate CR or PR, based on assessments per RECIST 1.1, DOR is defined as the time from first documented evidence of CR or PR until disease progression or death due to any cause, whichever occurs first.
- Disease Control Rate
  - DCR is defined as the percentage of subjects who have achieved CR, PR, or SD based on assessments per RECIST 1.1.
- Overall Survival (OS)
  - OS is defined as the time from first dose of study medication to death due to any cause.

### **13.6.2 Safety Endpoints**

The primary safety objective of this trial is to characterize the safety and tolerability of pembrolizumab in combination with azacitidine in subjects with advanced pancreatic ductal adenocarcinoma. The primary safety analysis will be based on subjects who experienced toxicities as defined by CTCAE criteria. Safety will be assessed by quantifying the toxicities and grades experienced by subjects who have received pembrolizumab, including serious adverse events (SAEs) and events of clinical interest (ECIs).

Safety will be assessed by reported adverse experiences using CTCAE, Version 4.0. The attribution to study treatment, time-of-onset, duration of the event, its resolution, and any concomitant medications administered will be recorded. AEs will be analyzed including but not limited to all AEs, SAEs, fatal AEs, and laboratory changes. Furthermore, specific immune-related adverse events (irAEs) will be collected and designated as immune-related events of clinical interest (ECIs) as described in [Section 10.4](#).

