## **9. DOSING DELAYS/DOSE MODIFICATIONS**

### **9.1. Dose Modification for Pembrolizumab**

Adverse events (both non-serious and serious) associated with pembrolizumab exposure may represent an immunologic etiology. These adverse events may occur shortly after the first dose or several months after the last dose of treatment. Pembrolizumab must be withheld for drug- related toxicities and

severe or life-threatening AEs as per Table 5 below. See [Section 8.3.6](#) for supportive care guidelines, including use of corticosteroids.

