#### **10.4. Events of Clinical Interest**

Selected non-serious and serious adverse events are also known as Events of Clinical Interest (ECI) and must be reported within 24 hours to the Sponsor-Investigator and within 2 working days to Merck Global Safety. (Attn: Worldwide Product Safety; [contact]).

For the time period beginning when the consent form is signed until treatment allocation/randomization, any ECI, or follow up to an ECI, that occurs to any subject must be reported within 24 hours to the Sponsor-Investigator and within 2 working days to Merck Global Safety if it causes the subject to be excluded from the trial, or is the result of a protocol-specified intervention, including but not limited to washout or discontinuation of usual therapy, diet, placebo treatment or a procedure.

For the time period beginning at treatment allocation/randomization through 90 days following cessation of treatment, or 30 days following cessation of treatment if the subject initiates new

anticancer therapy, whichever is earlier, any ECI, or follow up to an ECI, whether or not related to Merck product, must be reported within 24 hours to the Sponsor and within 24 hours to Merck Global Safety.

Events of clinical interest for this trial include:

- An overdose of Merck product, as defined in [Section 10.1 - Definition of an Overdose for This Protocol and Reporting of Overdose to the Sponsor-Investigator](#), that is not associated with clinical symptoms or abnormal laboratory results.
- An elevated AST or ALT lab value that is greater than or equal to 3X the upper limit of normal and an elevated total bilirubin lab value that is greater than or equal to 2X the upper limit of normal and, at the same time, an alkaline phosphatase lab value that is less than 2X the upper limit of normal, as determined by way of protocol-specified laboratory testing or unscheduled laboratory testing.\*
- **\*Note:** These criteria are based upon available regulatory guidance documents. The purpose of the criteria is to specify a threshold of abnormal hepatic tests that may require an additional evaluation for an underlying etiology.

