### **10.6. Assessing and Recording of Adverse Events**

An adverse event is defined as any untoward medical occurrence in a patient or clinical investigation subject administered a pharmaceutical product and which does not necessarily have to have a causal relationship with this treatment. An adverse event can therefore be any unfavorable and unintended sign (including an abnormal laboratory finding, for example), symptom, or disease temporally associated with the use of a medicinal product or protocol-specified procedure, whether or not considered related to the medicinal product or protocol-specified procedure. Any worsening (i.e., any clinically significant adverse change in frequency and/or intensity) of a preexisting condition that is temporally associated with the use of the Merck's product, is also an adverse event.

All adverse events that occur after the consent form is signed but before treatment allocation/randomization must be reported by the investigator if they cause the subject to be excluded from the trial, or are the result of a protocol-specified intervention, including but not limited to washout or discontinuation of usual therapy, diet, placebo treatment or a procedure.

From the time of treatment allocation/randomization through 30 days following cessation of treatment, all adverse events must be reported by the investigator. Such events will be recorded at each examination on the Adverse Event case report forms/worksheets. The reporting timeframe for adverse events meeting any serious criteria is described in section 10.8. The investigator will make every attempt to follow all subjects with non-serious adverse events for outcome.

Adverse events will not be collected for subjects during the pre-screening period (for determination of archival tissue status) as long as that subject has not undergone any protocol- specified procedure or intervention. If the subject requires a blood draw, fresh tumor biopsy, etc., the subject is first required to provide consent to the main study and AEs will be captured according to guidelines for standard AE reporting.

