### **15.6. Statistical Methods for Safety Analysis**

Safety and tolerability will be assessed by clinical review of all relevant parameters including adverse experiences (AEs), laboratory tests, and vital signs. Count and percentage AE will be provided. Confidence interval rate of AE of clinical interest will be estimated using Exact method based on binomial distribution.

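### Section 13.6.2 relies on Section 10.4 to say which immune-related events are ECIs, but 10.4 names none, so 90-day collection of the non-serious ones and exact intervals for all of them are undefined

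*Combined protocol and SAP*

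**What the plan says.** **Designation.** Section 13.6.2 states that specific irAEs will be collected and "designated as immune-related events of clinical interest (ECIs"), and gives Section 10.4 as the place where they are described. The word specific implies a defined set of terms.

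**Definition.** Section 10.4 opens its list with "Events of clinical interest for this trial include" and gives two entries. The first begins "An overdose of Merck product, as defined in" and is limited to overdoses without symptoms or abnormal laboratory results. The second begins "An elevated AST or ALT lab value that is greater than or equal to 3X the upper limit of normal" and also requires raised bilirubin with alkaline phosphatase below twice the upper limit of normal. No immune-related term appears.

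**Collection.** Sections 1.1 and 10.4 set the ECI window at 90 days after treatment, or 30 days if new anticancer therapy starts. Sections 1.1, 5.1 and 6.5.2 give serious adverse events 90 days in their own right. For the rest, Section 10.6 applies: "through 30 days following cessation of treatment, all adverse events must be reported by the investigator". Section 10.5 also uses 30 days.

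**Timing.** Section 9.1 says that adverse events of immunologic cause may appear soon after the first dose or "several months after the last dose of treatment".

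**Analysis.** Section 15.6 gives counts and percentages for adverse events in general, and then: "Confidence interval rate of AE of clinical interest will be estimated using Exact method based on binomial distribution".

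**The concern.** A cross-reference that leads nowhere is usually an editing matter. Here two operational rules hang on it. ECI status decides how long a non-serious event is collected after treatment and whether its rate is reported with an exact interval. Site staff work from the reporting section, 10.4; the analyst works from 13.6.2 and 15.6. As written they would act on different sets of events.

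Safety and tolerability of the combination is a stated secondary objective (Section 2.2), and irAEs are the class of event that 13.6.2 singles out. A missing interval can be added at analysis from the counts. A non-serious event that was never collected cannot be recovered. Section 8.2.5 adds to this: more than 30 days after the last dose, concomitant medication is recorded only for serious events and ECIs, so treatment given for a late non-serious irAE could also go unrecorded.

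**Working it through.** The plan states no ECI rate or interval, so there is no figure to reproduce. The check sets the sections side by side.

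**Step 1: does 10.4 supply the list?** Section 8.2.8 gives management guidance for 15 immune-related categories, not counting infusion reactions: hepatitis, pneumonitis, colitis, type 1 diabetes, hypophysitis, thyroid disorders, adrenal insufficiency, nephritis, dermatologic events, ocular events, pancreatitis, myocarditis, neuropathies, meningoencephalitis and myositis. None of the 15 is named in 10.4.

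**Step 2: does another route supply it?** Sections 9.1 and 10.2 (Anticipated Adverse Events) point to Section 8.3.6, a number that no section carries. Section 3.11, the parallel safety text, refers to 10.4 for ECIs without calling them immune-related. Section 8.2.6 allows systemic glucocorticoids for an ECI of suspected immune cause, so the plan assumes that such ECIs exist, but it does not list them.

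**Step 3: what follows under each reading?**

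| Event | Window if 13.6.2 governs | Window if the 10.4 list governs | Exact interval, 13.6.2 / 10.4 |
|---|---|---|---|
| Serious irAE | 90 days | 90 days (serious-event rule) | yes / not assured |
| Non-serious irAE | 90 days | 30 days | yes / not assured |
| Immune hepatitis meeting the liver criterion | 90 days | 90 days (ECI in its own right) | yes / yes |

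If new anticancer therapy starts, the ECI window is 30 days, and the two readings then agree on the window for non-serious irAEs.

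**Step 4: size of the gap.** 90 − 30 = 60 days, from day 31 to day 90. It concerns non-serious irAEs outside the liver criterion, in subjects who have not started new therapy. The documents give neither the rate of such events in that period nor the proportion of subjects starting new therapy, so the expected number missed cannot be calculated.

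**Step 5: what the interval in 15.6 would report.** With x events in n subjects, the exact 95% limits are the 0.025 quantile of Beta(x, n − x + 1) and the 0.975 quantile of Beta(x + 1, n − x). For an assumed x = 3:

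- n = 31: 3/31 = 9.7%, interval 2.0% to 25.8%.
- n = 37, the enrolment maximum in Section 6.4: 3/37 = 8.1%, interval 1.7% to 21.9%.

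These figures show the form of the output only. They do not measure what the gap loses.

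**The case against.** The best defence is that the plan does intend irAEs to be ECIs. Section 13.6.2 says so outright, 10.4 introduces its list with a verb that need not mean a complete list, and 8.2.6 speaks of ECIs of immune cause. On that reading the 90 days and the intervals already cover irAEs, and only the pointer needs repair. This stands in part: it rules out saying that the ECI rules plainly exclude irAEs. It does not say which irAEs qualify, which is what a site and an analyst need to know.

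Several limits also stand. Serious irAEs lose no collection time. An immune hepatitis that meets the liver criterion is an ECI already. Section 10.2.6 (Post-study Adverse Event) has subjects told at the last scheduled visit to report later events that may relate to participation. That is a route for late events, though a weak one next to required collection. All recorded events get counts and percentages, from which an exact interval can be computed. Finally, 90 days does not fully match the several months mentioned in 9.1.

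There is a fair objection to the obvious remedy as well. Section 10.4 attaches 24-hour reporting to ECIs after allocation, related or not. Adding all 15 categories there without qualification would expedite every low-grade event.

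**Conclusion.** The concern holds as an internal contradiction between 13.6.2 and 10.4, with consequences for collection and for 15.6. ECI status is undefined for irAEs. If 10.4 is applied as written, non-serious irAEs that begin on days 31 to 90 fall outside required collection, and exact intervals are not assured for irAEs, serious or not, beyond those that meet the liver criterion. This rests on the site following the list in 10.4 and on the subject not having started new anticancer therapy.

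A reader might infer three stronger things that the documents do not support.

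- That no irAE has 90-day collection: the serious-event rule contradicts this.
- That the only inferential safety analysis would concern overdoses and liver tests: 13.6.2 does designate irAEs as ECIs. Severe early immune events also count in the formal dose-limiting-toxicity rule of Sections 1.1 and 5.2.
- That the small sample shows how much is lost: the width of an exact interval describes sampling imprecision and says nothing about how many late events are missed.

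The primary endpoint, the sample size and the dose-limiting-toxicity decision are unaffected. The point still merits an amendment, because uncollected events cannot be restored at analysis.

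**What to change.** Reconcile Sections 13.6.2, 10.4 and 15.6:

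1. Name the irAE categories already set out in 8.2.8 as immune-related ECIs, in 10.4 or in a list to which both 10.4 and 13.6.2 point.
2. State that they are collected through 90 days after treatment, or 30 days if new anticancer therapy starts, whether serious or not.
3. State in 15.6 that exact binomial intervals are given for each category and for any irAE, and which of the safety populations in Section 15.2.2 is the denominator.
4. State separately whether the 24-hour reporting in 10.4 applies to these events, so that 90-day collection and analysis do not automatically expedite every low-grade event.
5. Correct the pointers to Section 8.3.6 in Sections 9.1 and 10.2.

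The cost is a protocol amendment and a modest amount of extra data collection and reporting between day 31 and day 90. No dose, schedule or management rule changes.

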### **13.6.3 Correlative Endpoints**

#### **13.6.3.1 Global DNA Methylation**

DNA methylation, using LINE-1 assay, will be determined and expressed as continuous variables with mean, median, and standard deviation calculations reported. Average changes in global DNA methylation will be assessed at baseline and every two weeks for the first eight weeks of the study. Disease control rates (DCR) and time to event endpoints (PFS and OS) will

be estimated for patients who have methylation below the median compared to above the median at baseline. We will also estimate these outcomes for those who achieve low methylation (<10% methylation) compared to normal methylation ( $\geq 10\%$  methylation) after eight weeks of therapy. We will also estimate these outcomes for those who achieve a change in methylation greater than the median compared to lower than the median at eight weeks compared to baseline.

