k. The first-on study tumor imaging will be performed after 8 weeks (± 7 days) of treatment, and will continue every 8 weeks (□□7 days) thereafter (or more frequently if clinically indicated). Timing of imaging follows calendar days and should not be adjusted due to dose interruptions. The same imaging technique, acquisition, and processing parameters for a subject should be used throughout the trial if possible.

l. Subjects without confirmed PD who discontinue treatment will have imaging performed at the time study treatment is discontinued (i.e. date of discontinuation □□4 week window). If a scan was obtained within 4 weeks prior to discontinuation of treatment, then imaging at treatment discontinuation is not required. Continue to monitor disease status as indicated in Section 6.6. Subjects who discontinue treatment after confirmed PD will not need further imaging performed during the follow-up period.

m. If archival tissue is not available then fresh biopsy is considered any tumor tissue collection within 42 days prior to first dose of study treatment and after previous therapy. All 31 subjects will have a newly-obtained biopsy during week 8 (□□7 days) of the study. An optional biopsy is also requested at the time of discontinuation for PD.

Trial Period:	Screening Phase	Treatment Cycles a										End of Treatment (last dose) or Discontinuation	Post-Treatment		
		Azacitidine (4 weeks per cycle)						Pembrolizumab (3 weeks per cycle)							
Treatment Week:		1	2	3	5	6	8	9	12	15	18		Safety Follow- Up (30 days from last dose) q	Follow Up Visits b (Q8W)	Survival Follow-Up (Phone)
Scheduling Window (Days):	-28 to -1	± 3	± 3	± 3	± 3	± 3	± 3	± 3	± 3	± 3	± 3			± 7	

n. Collect at baseline, and then on weeks 3, 5, and 6 prior to study treatment administration. Whole blood for Genetics/RNA and DNA analyses. Serum and plasma for Proteomics.  
o. The first dose of azacitidine is Week 1 Day 1, other doses have a +/-3 day window for dose administrations (for azacitidine as well as pembrolizumab). Azacitidine will be dosed on 5 consecutive business days. On the days when azacitidine is given with pembrolizumab, the pembrolizumab will be administered first followed by azacitidine.  
p. Screening ECOG should be performed within 3 days prior to first dose of study therapy.  

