**12.1.6.6                    Tumor Tissue Collection and Correlative Studies Blood Sampling**

All patients will have tumor biopsy specimens obtained at baseline prior to study drug administration and then during week 8 to assess methylation status and immune response. Peripheral blood will be evaluated for methylation status at baseline and then prior to treatment administration on weeks 3, 5, and 6.

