#### **15.2.7 Exploratory and Ancillary Studies**

See [Section 13.6.3](#) for description of correlative studies. All subjects will be required to agree to an on treatment biopsy after 8 weeks of therapy. Given the patient population and the likelihood that some subjects will have disease or clinical progression precluding biopsies we estimate that we will obtain on-treatment biopsy samples from a minimum of 20 subjects.

- 15.2.7.1 Global DNA Methylation will be assessed in all subjects at baseline and every 2 weeks for the first 8 weeks of study. We will estimate the disease control rates (DCR) and time to event endpoints (median PFS and median OS) for subjects who have methylation below the median compared to above the median at baseline. We will also estimate these outcomes for those who achieve low methylation (<10% methylation) compared to normal methylation ( $\geq 10\%$  methylation) after 8 weeks of therapy. We will also estimate these outcomes for those who achieve a change in methylation greater than the median compared to higher than the median at 8 weeks (compared to baseline).
- 15.2.7.2 Fisher's exact test will be performed to compare the disease control rate for the two groups. Kaplan-Meier estimates of the survival distribution for the two groups will be calculated, and the two groups will be compared using a log-rank test. Change in methylation in tumor tissue will be evaluated in 20 patients who undergo baseline and week eight biopsies and will be compared using the paired t-test or the Wilcoxon signed-rank test depending on the data distribution. With 20 patients, we will have 80% power to detect a change of 0.66 standard deviations given an alpha of 0.05.
- 15.2.7.3 Change in methylation in tumor tissue will be evaluated in subjects who undergo baseline and week 8 biopsies. We will describe changes in specific gene methylation patterns as described in [Section 13.6.3](#).
- 15.2.7.4 Immune phenotyping will be measured on the subjects who undergo an on-treatment tumor biopsy. We will provide descriptive tables of IHC expression of CD8/CD3 T cell ratio, CD86/CD68 macrophage ratio, PD1 expression. Samples will be compared between pre and post combination specimens in treated subjects using the paired t-test.

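### Two of the three planned methylation groupings need an eight-week value, but no eight-week blood draw is scheduled and the sample type is not named

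*Combined protocol and SAP*

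**What the plan says.** **Analysis.** Section 13.6.3.1 specifies the LINE-1 assay, with average changes to be assessed at baseline and "every two weeks for the first eight weeks of the study". Section 15.2.7.1 agrees: "Global DNA Methylation will be assessed in all subjects at baseline and every 2 weeks for the first 8 weeks of study". DCR, PFS and OS are to be estimated under three groupings:

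1. Baseline methylation above or below the median.
2. Level after eight weeks, cut at 10%: "We will also estimate these outcomes for those who achieve low methylation (<10% methylation) compared to normal methylation".
3. Change, split "greater than the median compared to lower than the median at eight weeks compared to baseline".

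Section 15.2.7.2 adds Fisher's exact test for DCR and log-rank tests for the time-to-event outcomes. Neither 13.6.3.1 nor 15.2.7.1 names the sample type.

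**Collection.** Section 12.1.6.6 states: "Peripheral blood will be evaluated for methylation status at baseline and then prior to treatment administration on weeks 3, 5, and 6". Footnote n of the flow chart in section 12.1 gives the same times: "Collect at baseline, and then on weeks 3, 5, and 6 prior to study treatment administration". The correlative-blood row of the flow chart marks those visits and end of treatment or discontinuation; its week-8 cell is empty. For tissue, section 12.1.6.6 states: "All patients will have tumor biopsy specimens obtained at baseline prior to study drug administration and then during week 8".

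**The concern.** The analysis sections and the collection schedule describe different sampling plans, and two of the three groupings rest on the time point that blood collection omits.

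Methylation in tumour and blood is a named exploratory objective (section 2.3), and priming by hypomethylation is the rationale for the regimen (section 3.5). If the mismatch stays, someone must choose a substitute time point, sample type or assay in an open-label, single-arm trial, probably after PFS is known. The available draws are not interchangeable. Azacitidine is given in weeks 1, 5 and 9, so the week-5 draw precedes the second course and the week-6 draw comes directly after it. A sample that was never drawn cannot be recovered.

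**Working it through.** **The plan's own figure.** No power is stated for the blood groupings. The one figure in the methylation plan (section 15.2.7.2) is for paired tumour tissue: 20 subjects, a change of 0.66 SD, alpha 0.05, 80% power. For a two-sided paired t-test the noncentrality is 0.66 × √20 = 2.95 on 19 degrees of freedom, and the exact power is 0.799. The figure reproduces, and it does not depend on blood sampling.

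**Step 1, sample type.** Tissue is taken at baseline and week 8 only, so a two-weekly series in all subjects cannot be tissue. Blood is the only workable reading. If tissue was meant, the two-weekly schedule fails anyway.

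**Step 2, days.** Day 1 of study week w is day 7(w − 1) + 1. The draws in weeks 3, 5 and 6 are therefore on days 15, 29 and 36, each with the ±3 day window of the flow chart. An interval of k elapsed weeks ends on day 1 + 7k, so 2, 4, 6 and 8 weeks are days 15, 29, 43 and 57. Read as study weeks, 2, 4, 6 and 8 are days 8–14, 22–28, 36–42 and 50–56.

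| Reading of two-weekly | 2 | 4 | 6 | 8 |
|---|---|---|---|---|
| Elapsed weeks, ±3 days | week-3 draw | week-5 draw | none | none |
| Study weeks, nominal days | none | none | week-6 draw | none |
| Study weeks, ±3 days | week-3 draw | week-5 draw | week-6 draw | none |

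With baseline added, coverage is 3, 2 or 4 of the 5 planned points. Only the last column is the same on every reading.

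**Step 3, the eight-week gap.** The latest on-treatment draw is day 36 + 3 = 39. Study week 8 begins on day 50, which is 50 − 39 = 11 days later; eight elapsed weeks is day 57, which is 57 − 39 = 18 days later. If the blood value were allowed the ±7 day window of the week-8 biopsy, the earliest day would be 50 − 7 = 43, still 4 days after the latest draw.

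**Step 4, groupings.** Baseline: supported. Eight-week level: not supported. Change to eight weeks: not supported. That is two of three.

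**Step 5, other samples.** The end-of-treatment draw comes at a different time in each subject, so it gives no common eight-week value. The week-8 biopsy is assigned in section 13.6.3.2 to an array platform, not LINE-1. Section 15.2.7 expects on-treatment tissue from a minimum of 20 subjects, whereas 15.2.7.1 plans the assessment for all subjects.

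**The case against.** The strongest reply is that the two schedules are closer than they look. Pembrolizumab starts two weeks after azacitidine (section 1.1), and that visit is called week 3 (section 5.1 and Table 3). The week-3 and week-5 draws are therefore the 2- and 4-week points under another label. This stands. A reader might infer that only baseline and week 6 are covered, 2 of 5 points, but that count holds only if elapsed intervals and study weeks are treated as the same and the visit window is ignored.

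The flow chart also marks a draw at discontinuation. The first scan is due at 8 weeks, so a subject who stops at that scan could have blood taken near week 8. A reader might infer that no subject would have a blood sample near that time; the documents do not support this. Such samples would come from subjects who are stopping treatment, however, so they cannot form the planned groups.

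Finally, an eight-week methylation value is planned, in tumour. That is true, but it comes from another assay, in fewer subjects. Section 15.2.7 gives disease or clinical progression as the reason some biopsies will be missing, so the gaps are related to the outcomes being compared. The biopsy does not stand in for the blood analysis described.

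**Conclusion.** The point holds in a limited form. On every reading of the calendar, the eight-week level and eight-week change groups cannot be formed from scheduled blood, and the sections that define them omit the sample type. Two of three exploratory groupings are affected.

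A reader might go further and infer that the pharmacodynamic test of the priming hypothesis fails as a whole. The documents do not support that. The paired baseline and week-8 tumour methylation analysis with its power statement, immune phenotyping on the biopsies, and the baseline-methylation grouping are untouched, as are the primary and secondary endpoints.

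The conclusion assumes that the two-weekly series is blood, that week 1 day 1 is the first azacitidine dose, and that draws fall on day 1 of their study week within ±3 days. It should be corrected, but it does not bear on the trial's main result.

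**What to change.** State in 13.6.3.1 and 15.2.7.1 that the sample is peripheral blood. Then, before data are seen, make schedule and analysis agree in one of two ways.

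**(a) Move the week-6 correlative draw to the week-8 scan and biopsy visit.** Amend the flow-chart row, footnote n and section 12.1.6.6, and replace the two-weekly wording in 13.6.3.1 and 15.2.7.1 with the actual draws. No dose falls in week 8, so the wording that ties each draw to the time before treatment needs adjusting for this one. This keeps the eight-week groups and their alignment with the biopsy. The cost is the loss of the week-6 value.

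**(b) Keep the draws.** Replace the time points in 13.6.3.1 and 15.2.7.1 with baseline and weeks 3, 5 and 6, and define the level and change groups at week 6. Only those two sections change. The text should note that week 6 comes directly after the second azacitidine course and is not aligned with the week-8 biopsy, so the groups answer a somewhat different question.

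Neither option adds a draw or a visit. Option (a) preserves the planned question. Option (b) is the cleaner choice if subjects have already been sampled under the present schedule. In the same amendment, correct the change split in 15.2.7.1, which names the upper side of the median twice, to match 13.6.3.1.
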